5.4.2. Estimated Glomerular Filtration Rate

Kidney function evaluated by eGFR will be summarized at baseline and each postbaseline time point by treatment group using descriptive statistics for the observed value as well as the change from baseline and percentage change from baseline.

For participants in the LN cohort, baseline eGFR will be defined as the lowest measurement available prior to the first dose of study intervention. Screen failed values will not be considered.

For participants in the IgAN cohort, baseline eGFR will be defined as the mean of the Screening and Day 1 measurements.

For participants requiring dialysis for acute kidney injury, a value of 10 mL/min/1.73 m² will be imputed for while participants are on dialysis (ie, from the first day of dialysis through 5 days after the end of dialysis).

The longitudinal changes in eGFR will also be analyzed using the same MMRM method specified in Section 5.4.1.

This analysis will be performed 2 ways:

- Data collected on or after receipt of additional standard-of-care therapy (for the LN cohort only) will be imputed using the value collected at the time of renal flare, extrarenal SLE flare, suboptimal response, and data collected on or after treatment discontinuation will be assumed missing and handled in the MMRM as MAR.
- Data collected on or after receipt of additional standard-of-care therapy or treatment discontinuation will be assumed missing and handled in the MMRM as MAR.

The trajectory of eGFR over time will be visually presented by plotting the mean eGFR at each time point by treatment group.

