5. STATISTICAL ANALYSES

5.1. General Considerations

All data collected in this study will be presented separately by disease cohort using summary tables, figures, and data listings. All analyses will be performed using Statistical Analysis Software® (SAS) release, V 9.4 or higher (SAS Institute Inc., Cary, NC, USA) or other validated statistical software.

All efficacy and safety analyses will be summarized separately for the Initial Evaluation Period, Extension Period, and Post-treatment Follow-up Period. Limited data will be collected during the Post-treatment Follow-up Period and will be summarized descriptively, as appropriate.

The analyses for participants in the LN cohort and participants with IgAN cohort will be conducted and reported separately.

Continuous variables will be summarized using descriptive statistics, including number of observations and mean, SD, median, minimum, and maximum values. Categorical variables will be summarized by frequency counts and percentage of patients.

Unless otherwise specified, data collected at an unscheduled visit will be included in by-patient listings but not in the summary tabulations. However, unscheduled study visits will be used in the calculation of baseline values.

Summaries of study and participant characteristics (eg, demographics and baseline characteristics, medical history, protocol deviations) are described in Section [6.2](#).

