Secondary (key continuous endpoints)	Ravulizumab or placebo	Full Analysis Set	Percentage change from baseline to Week 50 in proteinuria (both cohorts) Change from baseline in eGFR at Week 26 and Week 50 (both cohorts)	Data on or after receipt of additional standard-of-care therapy (LN cohort only) will be imputed using the value collected at the time of renal flare or severe extrarenal SLE flare (or suboptimal after Week 26, if applicable) Data on or after treatment discontinuation will be assumed missing and handled in the MMRM as MAR	Mean of the variable in each treatment group

Table 1: Estimands

Estimand	Treatment	Population	Variable	Handling of IE	Summary Measure
Secondary (key binary endpoints)	Ravulizumab or placebo	Full Analysis Set	
Percentage of participants with > 30% and > 50% reduction in proteinuria at Week 26 and Week 50 compared to baseline (both cohorts)
 
Percentage of participants meeting the criteria for CRR at Week 26 and Week 50 (LN cohort only)
 
Percentage of participants meeting the criteria for PRR at Week 26 and Week 50 (LN cohort only)
 
Percentage of participants meeting the criteria for Partial Remission at Week 26 and Week 50 (IgAN cohort only)
	
Participants who receive additional standard-of-care therapy (LN cohort only) or discontinue treatment are assigned as nonresponders
	Proportion of the variable in each treatment group

Abbreviations: CRR = complete renal response; eGFR = estimated glomerular filtration rate; IE = intercurrent events; LN = lupus nephritis; MAR = missing-at-random; MMRM = mixed effect model for repeated measures; PK = pharmacokinetics; PRR = partial renal response

The secondary estimands for all other secondary endpoints are similar to above except the intercurrent events will be ignored and all data occurring on or after the intercurrent event will be analyzed as observed.

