5.4.4. Complete Renal Response (LN Cohort Only)

For the LN cohort, CRR is defined as meeting all 3 of the following criteria:

- A decrease in mean UPCR to ≤ 0.5 g/g based on two 24-hour urine collections obtained within 2 weeks prior to the study visit (Week 26 or Week 50).
- $eGFR > 60$ mL/min/1.73 m² or no eGFR reduction $\geq 20\%$ from the baseline value based on the mean of 2 values. The first eGFR value must be obtained within 2 weeks prior to the study visit (Week 26 or Week 50), and the second eGFR value will be obtained on the study visit (Week 26 or Week 50).
- No treatment failure (as defined in Section 5.4.11).

Participants who receive additional standard-of-care therapy, discontinue treatment prior to the endpoint assessment or study withdrawal will be considered nonresponders.

The percentage of participants meeting the criteria for CRR as well as individual components of CRR will be analyzed using a CMH test accounting for the stratification factor at Week 26 and Week 50 and will be summarized by treatment group by calculating the point estimate and 2-sided 95% CI based on exact confidence limits using the Clopper-Pearson method.

A bar chart will also be provided displaying the proportion of participants meeting the criteria for CRR as well as individual components of CRR at Week 26 and Week 50 by treatment group.

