6.1.2. Definition of Baseline Values

For the Initial Evaluation Period, baseline is defined as the last available assessment value prior to the first dose of study intervention. For the Extension Period, baseline is defined as the last available assessment prior to the first dose of study intervention administered in the Extension Period.

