6.1.9. CRR (LN Cohort Only)

CRR is defined as meeting all 3 of the following criteria:

- A decrease in mean UPCR to ≤ 0.5 g/g
- eGFR > 60 mL/min/1.73 m² or no eGFR reduction $\geq 20\%$ from the baseline value
- No treatment failure

Only central laboratory results from both scheduled and unscheduled visits will be used to assess CRR.

Proteinuria values will meet the criteria for CRR if the mean of two 24-hour UPCR values at the scheduled visit (Week 26 or Week 50) and within 2 weeks prior to the scheduled visit, determined using the actual date of the measurement taken, is ≤ 0.5 g/g.

In the presence of missing central laboratory values, the following rules will be applied:

- If only 1 nonmissing 24-hour urine collection is available at the visit, then this value will be used for analysis.
- If both collections are missing at the visit, then CRR will be treated as nonresponder.

eGFR values will meet the criteria for CRR if the mean of 2 collections at the scheduled visit (Week 26 or Week 50) and within 2 weeks prior to the scheduled visit, determined using the actual date of the measurement taken, is > 60 mL/min/1.73 m² or result in a reduction from baseline that is $< 20\%$.

In the presence of missing central laboratory values, the following rules will be applied:

- If only 1 value is available at the visit, then this value will be used for analysis.
- If both values are missing at the visit, then CRR will be treated as nonresponder.

No treatment failure will be determined as the absence of additional standard-of-care therapy received at any time up to Week 26 or Week 50 for protocol-defined renal flare, severe extrarenal SLE flare, or suboptimal response as recorded on the Rescue Therapy eCRF.

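### Taking the lowest pre-dose eGFR as the LN baseline biases the within-arm eGFR change upward in both arms; the treatment comparison is not biased

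*SAP*

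**What the plan says.** The SAP contains three rules for a baseline that could apply to eGFR.

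- LN cohort, SAP 5.4.2: "baseline eGFR will be defined as the lowest measurement available prior to the first dose of study intervention". Values from a failed screening are excluded.
- IgAN cohort, same section: "baseline eGFR will be defined as the mean of the Screening and Day 1 measurements".
- General rule, SAP 6.1.2: "For the Initial Evaluation Period, baseline is defined as the last available assessment value prior to the first dose of study intervention".

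Protocol Table 1 schedules LN eGFR at Screening and on Day 1, up to six weeks apart. SAP 5.1 adds that "unscheduled study visits will be used in the calculation of baseline values", so some LN participants will have three or more candidate values.

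The LN baseline feeds the by-arm summaries of "change from baseline and percentage change from baseline" and the MMRM in SAP 5.4.2. SAP Table 1 lists eGFR change among the key continuous secondary endpoints, with summary measure "Mean of the variable in each treatment group". Protocol 4.2.2 also calls change in eGFR a key secondary endpoint.

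CRR and PRR (SAP 5.4.4, 5.4.5, 6.1.9, 6.1.12) each include an eGFR component that is met in either of two ways: eGFR above 60, or a fall of less than 20% "from the baseline value based on the mean of 2 values". None of these sections says which baseline is meant. The protocol gives no eGFR-specific baseline, and no reason for choosing the lowest value appears in either document.

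**The concern.** A minimum is selected for being low. Part of what makes it low is measurement noise, and that part is not expected to recur at the next visit. Change from a minimum to an ordinary follow-up value is therefore positive on average even when nothing has happened. The shift grows with the number of pre-dose readings, so a participant with an unscheduled draw carries more of it.

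The affected quantity is the one SAP Table 1 names for eGFR: the mean in each arm. A reader of the LN results could see both arms appear to gain kidney function and take that as recovery. The protocol (9.5.2) says the Week 26 analysis will inform Phase 3 planning, so an inflated within-arm figure could be carried forward.

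There is also an internal mismatch. Serum creatinine has no special rule, so its baseline is the last value under SAP 6.1.2. An LN participant's baseline creatinine and baseline eGFR can then come from different dates, although one is calculated from the other and both define subgroups in SAP 5.7.4.

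**Working it through.** The plan states no figure to reproduce here, and no SD or CV for eGFR. The inputs are the two scheduled readings (Protocol Table 1), the LN rule (SAP 5.4.2) and the 20% limit (SAP 5.4.4). The within-person CV is an assumption, shown at 5%, 10% and 15%. Readings are taken as independent, normal and of equal SD around a stable true level.

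**Step 1: shift of the minimum.** For two readings, E[min] = true level − SD/√π = true level − 0.564 SD. For three readings the constant is 0.846, which is 1.5 times larger.

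**Step 2: spurious mean gain, no true change.** Gain = constant × CV × eGFR, in mL/min/1.73 m². Example: 0.564 × 0.10 × 75 = 4.2.

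| CV | eGFR 60, two readings | eGFR 75, two readings | eGFR 90, two readings | eGFR 75, three readings |
|---|---|---|---|---|
| 5% | +1.7 | +2.1 | +2.5 | +3.2 |
| 10% | +3.4 | +4.2 | +5.1 | +6.3 |
| 15% | +5.1 | +6.3 | +7.6 | +9.5 |

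**Step 3: does adjustment help?** About 600,000 participants were simulated with no treatment effect, two pre-dose values and a two-value follow-up mean. A single-visit ANCOVA stood in for the MMRM.

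- With the lowest value and a true mean set at 75, the mean change was +2.17, +4.35 and +6.49 for the three CVs. The adjusted mean was identical each time, so the covariate does not remove the bias.
- The mean percentage change was about +3%, +7% and +11%.
- With the mean of two values, or the last value, the mean change was between −0.09 and +0.01 across all scenarios, including true mean 60.
- The between-arm difference stayed within 0.04 of zero under every rule.

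**Step 4: the 20% limit, if the lowest value is used there.** The expected true fall at which the limit sits is 1 − 0.8 × (1 − 0.564 × CV).

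- CV 5%: 1 − 0.8 × 0.9718 = 22.3%
- CV 10%: 1 − 0.8 × 0.9436 = 24.5%
- CV 15%: 1 − 0.8 × 0.9154 = 26.8%

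**Step 5: when that limit decides anything.** A participant with eGFR above 60 passes regardless. If the baseline is 75 or more, a fall of less than 20% leaves eGFR above 0.8 × 75 = 60, so the 20% leg adds nothing. It decides only when follow-up eGFR is 60 or below.

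**Step 6: effect on the eGFR component as a whole.**

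- Among participants with a true 25% fall (mean 75, CV 10%), 68% pass with the lowest value, 56% with the mean and 59% with the last value.
- In a broader population (true eGFR mean 75, SD 25, limited to 30–130; CV 10%; no average change; SD of true change 10% or 20%), the lowest value raises the pass rate over the mean by about 1.4 or 2.6 percentage points.
- Across means of 60 to 90 and CVs of 5% to 15%, the gap is about 0.3 to 5.2 points.

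CRR and PRR also require the UPCR criterion and no treatment failure, so the effect on full response rates is smaller again.

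**The case against.** The strongest reply is that the rule is fixed before randomization and is the same in both arms. The study objective is a comparison with placebo, the eGFR MMRM follows a method that for LN proteinuria ends in a treatment contrast, and CRR is tested by a stratified CMH test. A reader might infer that the baseline rule favours ravulizumab or inflates the error rate of these comparisons. It does neither, and that part of the objection stands in full. It does not rescue the within-arm mean, which is the summary measure the SAP names.

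Second, Screening and Day 1 may not be exchangeable. LN participants have active disease, and those not already on corticosteroid induction receive methylprednisolone during Screening (Protocol 6.5.1), so eGFR may be moving. If it is falling, the lowest value tends to be the last one, as under SAP 6.1.2. If it is rising, the lowest value counts the pre-dose recovery as on-study gain, and the mean counts part of it. This stands as a limit on the size of the bias and bears on the choice of replacement.

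Third, the link to CRR and PRR is inferred. SAP 5.4.2 holds the only LN-specific eGFR definition, but the response sections do not cite it and 6.1.2 gives another. This also stands. A reader might go further and conclude that falls above 20% pass because of the baseline rule. Many pass by design under any rule: a fall from 120 to 61 qualifies through the first leg.

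Finally, a reader might object that LN and IgAN changes become non-comparable. The plan analyses and reports the cohorts separately and plans no such comparison. Different cohort rules are not in themselves an error.

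**Conclusion.** The concern holds for within-arm LN results. If pre-dose eGFR is stable, the lowest-value rule biases the mean change upward in both arms by 0.56 within-person SD with two readings and 0.85 with three. At eGFR 75 with two readings that is roughly 2 to 6 mL/min/1.73 m² over the assumed CV range. The direction follows from the definition; the size depends on a CV the documents do not give.

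The primary endpoint, the between-arm eGFR difference and the type I error of the CRR test are unaffected. The documents do not support a claim of materially inflated CRR or PRR rates: the link to that baseline is unstated, and the 20% leg decides only at follow-up eGFR of 60 or below. What remains there is an ambiguity that should be closed. The point deserves correction because it distorts a named key secondary summary, no rationale is offered, and the SAP already contains two rules that avoid the distortion when pre-dose eGFR is stable.

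**What to change.** In SAP 5.4.2, define LN baseline eGFR either as the mean of the Screening and Day 1 values, as for IgAN, or as the last pre-dose value, as in 6.1.2. Apply it to change and percentage change from baseline, the MMRM covariate and the eGFR criterion for CRR and PRR. Name that baseline explicitly in 5.4.4, 5.4.5, 6.1.9 and 6.1.12, and make 5.4.2 and 6.1.2 consistent. Keep the lowest value, if wanted, only as a sensitivity analysis.

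Between the two options, the mean is less noisy when pre-dose eGFR is stable. If eGFR is already recovering during Screening, the mean still counts part of that recovery as on-study gain, and the last value does not.

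The cost is SAP wording and programming; no new data are needed. The LN descriptive eGFR changes, and the CRR and PRR rates if they use this baseline, will look slightly less favourable.

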5.4.3. Serum C3 and C4 Concentrations

Serum C3 and C4 concentrations will be summarized at baseline and each postbaseline time point by treatment group using descriptive statistics for the observed value as well as the change from baseline. There will be no imputation for missing data or data collected on or after the receipt of additional standard-of-care therapy (for LN cohort) or treatment discontinuation.

The trajectory of serum C3 and serum C4 over time will be visually presented by plotting the mean values at each time point by treatment group.

5.4.4. Complete Renal Response (LN Cohort Only)

For the LN cohort, CRR is defined as meeting all 3 of the following criteria:

- A decrease in mean UPCR to ≤ 0.5 g/g based on two 24-hour urine collections obtained within 2 weeks prior to the study visit (Week 26 or Week 50).
- $eGFR > 60$ mL/min/1.73 m² or no eGFR reduction $\geq 20\%$ from the baseline value based on the mean of 2 values. The first eGFR value must be obtained within 2 weeks prior to the study visit (Week 26 or Week 50), and the second eGFR value will be obtained on the study visit (Week 26 or Week 50).
- No treatment failure (as defined in Section 5.4.11).

Participants who receive additional standard-of-care therapy, discontinue treatment prior to the endpoint assessment or study withdrawal will be considered nonresponders.

The percentage of participants meeting the criteria for CRR as well as individual components of CRR will be analyzed using a CMH test accounting for the stratification factor at Week 26 and Week 50 and will be summarized by treatment group by calculating the point estimate and 2-sided 95% CI based on exact confidence limits using the Clopper-Pearson method.

A bar chart will also be provided displaying the proportion of participants meeting the criteria for CRR as well as individual components of CRR at Week 26 and Week 50 by treatment group.

5.4.5. Partial Renal Response (LN Cohort Only)

For the LN cohort, PRR is defined for participants not achieving CRR as meeting all 3 of the following criteria:

- A decrease in UPCR $> 50\%$ compared to the baseline value based on mean of two 24-hour urine collections obtained within 2 weeks prior to the study visit (Week 26 or Week 50).
- eGFR $> 60 \text{ mL/min/1.73 m}^2$ or no eGFR reduction $\geq 20\%$ from the baseline value based on the mean of 2 values. The first eGFR value must be obtained within 2 weeks prior to the study visit (Week 26 or Week 50) and the second eGFR value will be obtained on the study visit (Week 26 or Week 50).
- No treatment failure (as defined in Section [5.4.11](#)).

Participants who receive additional standard-of-care therapy, who discontinue treatment prior to the endpoint assessment or study withdrawal will be considered nonresponders.

The percentage of participants meeting CRR, PRR, and no renal response will be summarized by treatment group by calculating the point estimate and 2-sided 95% CI based on exact confidence limits using the Clopper-Pearson method.

5.4.6. Time to UPCR $\leq 0.5 \text{ g/g}$ (LN Cohort Only)

For the LN cohort, time to UPCR $\leq 0.5 \text{ g/g}$ will be summarized based on spot urine samples. Participants will be assigned as responders at the time of achievement of UPCR $\leq 0.5 \text{ g/g}$ or censored at the earliest of their treatment discontinuation time, receipt of additional standard-of-care therapy, study withdrawal, or death or at Week 50 if they have not responded or received additional standard-of-care therapy by then. Participants with baseline spot UPCR $\leq 0.5 \text{ g/g}$ will be excluded from the analysis.

A Kaplan-Meier cumulative distribution curve will be generated for treatment group, and a log-rank test comparing the curves will be performed. The corresponding summary table will present by treatment group the cumulative distribution function (CDF) estimate, the number of participants at risk, the number of participants responding, and the number of participants censored at each postbaseline time point. The table will also present the first quartile, median, and third quartile, along with 2-sided 95% CI, of time to UPCR $\leq 0.5 \text{ g/g}$.

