5.1.4. Handling of Dropouts or Missing Data

No imputation will be performed for missing baseline values.

To derive duration of disease, partial date of diagnosis will be imputed. If Day is missing, then impute to the 1st. If Day and Month are missing, then impute to Jan 1st. Concomitant medication start date and AE start date will follow the same imputation rule to derive the study phase.

Missing data for QoL instruments will be handled as specified in the instructions for each instrument in Section [6.3](#).

In addition, the following intercurrent events may occur during the study:

1. Receipt of additional standard-of-care therapy (LN cohort only)
2. Treatment discontinuation

For the primary efficacy endpoint, only data up to the point of additional standard-of-care therapy will be included as observed. For participants in the LN cohort who receive additional standard-of-care therapy, the proteinuria value from the 24-hour urine collection performed at the time of renal flare or severe extrarenal SLE flare will be carried forward to subsequent visits. Data occurring on or after treatment discontinuation will be assumed missing-at-random (MAR) and imputed using multiple imputation as described in Section [5.3.2](#). For participants who experience multiple intercurrent events, data will be handled according to the first intercurrent event.

Additional sensitivity analyses are specified in Section [5.3.3](#).

For secondary responder endpoints, participants who receive additional standard-of-care therapy or discontinue treatment are assigned as nonresponders regardless of whether there is any response observed after these protocol-defined intercurrent events. For missing postbaseline data not due to intercurrent events, no imputation will be performed.

A summary of the primary and secondary estimands for this study is provided in [Table 1](#).

Table 1: Estimands

Estimand	Treatment	Population	Variable	Handling of IE	Summary Measure
Primary	Ravulizumab or placebo	Full Analysis Set	Percentage change from baseline to Week 26 in proteinuria (both cohorts)	Data on or after receipt of additional standard-of-care therapy (LN cohort only) will be imputed using the value collected at the time of renal flare or severe extrarenal SLE flare Data on or after treatment discontinuation will be imputed using multiple imputation	Difference in mean of the variable between treatment groups

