5.5.5. Time to CRR and PRR (LN Cohort Only)

For the LN cohort, time to CRR and time to PRR will be summarized using spot urine samples. Participants will be assigned as responders at the time of their CRR or PRR, respectively, or censored at the earliest of their treatment discontinuation time, receipt of additional standard-of-care therapy, study withdrawal or death, or at Week 50 if they have not responded or received additional standard-of-care therapy by then.

Kaplan-Meier cumulative distribution curves will be generated for each treatment group, and a log-rank test comparing the curves will be performed. A corresponding summary table will present the CDF estimate, the number of participants at risk, the number of participants responding, and the number of participants censored at each postbaseline time point by treatment group. The table will also present first quartile, median, and third quartile, along with corresponding 2-sided 95% CI, of time to response.

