5.5.7. Time to UPCR > 50% Decrease (LN Cohort Only)

For the LN cohort, time to UPCR > 50% decrease from baseline will be summarized using spot urine samples. Participants will be assigned as responders at the time of their > 50% decrease from baseline in UPCR or censored at the earliest of their treatment discontinuation time, receipt of additional standard-of-care therapy, study withdrawal or death, or at Week 50 if they have not responded or received additional standard-of-care therapy by then.

Kaplan-Meier cumulative distribution curves will be generated for each treatment group, and a log-rank test comparing the curves will be performed. A corresponding summary table will present the CDF estimate, the number of participants at risk, the number of participants responding, and the number of participants censored at each postbaseline time point by treatment group. The table will also present first quartile, median, and third quartile, along with corresponding 2-sided 95% CI, of time to response.

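### LN time-to-response analyses: censoring at additional therapy breaks the SAP's stated rule for time to UPCR ≤ 0.5 g/g, and for CRR/PRR (and for death in all three) the Kaplan-Meier curve exceeds the share who can respond

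*SAP*

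**What the plan says.** Below, *rescue* is shorthand for additional standard-of-care therapy.

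**Censoring.** SAP 5.4.6 (time to UPCR ≤ 0.5 g/g, a secondary LN endpoint) has participants "censored at the earliest of their treatment discontinuation time, receipt of additional standard-of-care therapy, study withdrawal, or death or at Week 50". SAP 5.5.5 (time to CRR and PRR, exploratory) has them "censored at the earliest of their treatment discontinuation time, receipt of additional standard-of-care therapy, study withdrawal or death, or at Week 50". SAP 5.5.7 (time to a > 50% UPCR decrease, exploratory) uses the same rule: "censored at the earliest of their treatment discontinuation time, receipt of additional standard-of-care" and so on. In 5.4.6, "A Kaplan-Meier cumulative distribution curve will be generated for treatment group, and a log-rank test comparing the curves will be performed"; the two exploratory sections do the same. No competing-risk estimate is planned.

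**Rules elsewhere for the same events.**
- The note under Table 1 in SAP 5.1.4 says that for all other secondary endpoints "the intercurrent events will be ignored and all data occurring on or after the intercurrent event will be analyzed as observed". Table 1 does not name time to UPCR ≤ 0.5 g/g, so the note covers it.
- For secondary responder endpoints, SAP 5.1.4 says "participants who receive additional standard-of-care therapy or discontinue treatment are assigned as nonresponders". SAP 5.4.4, 5.4.5 and 5.5.6 apply this to CRR, PRR and overall renal response, and add study withdrawal.
- SAP 6.1.9 and 6.1.12 make absence of treatment failure, meaning no rescue, one of the three criteria for CRR and for PRR.

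**Protocol.** Protocol 9.4.5.1 itself censors the exploratory time-to-response endpoints at discontinuation and rescue. Protocol 9.4.1.2.2 gives no censoring rule for time to UPCR ≤ 0.5 g/g. SAP 6.5 (Appendix 5) lists only the hematuria change.

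**The concern.** Reading the complement of a Kaplan-Meier curve as the share who respond requires that censored participants would have gone on to respond at the same rate as those still at risk. Here that is doubtful, because the rescue triggers are measured on the outcome variable. Suboptimal Response (SAP 5.4.10) is proteinuria reduced by no more than 25%. With entry UPCR of at least 1 g/g, such a participant has a 24-hour UPCR of at least 0.75 × 1 = 0.75 g/g, above the 0.5 g/g target. Renal Flare (SAP 5.4.8) includes a doubling of UPCR.

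For CRR and PRR the problem is one of definition: rescue rules response out, yet the censored participant is counted as still able to respond. Death has the same effect on every endpoint.

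At stake are the reported cumulative response, its quartiles and the visual comparison of arms. For time to UPCR ≤ 0.5 g/g there is also the question of which estimand the SAP has committed to, since two of its passages give different answers.

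**Working it through.** The documents give no event rate, hazard or power for these endpoints, so there is no planned figure to reproduce. The size has to be shown over assumed ranges.

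**Inputs.** Allocation is 40 ravulizumab to 20 placebo (SAP 3). As background only, Protocol 2.2.1 cites renal flare in up to 25% of patients within 1 year, and CRR in 10% to 40% after 6 to 12 months of standard of care. Assumed: p, the Week 50 share who respond with failures counted as nonresponse, of 20% to 50%; and q, the share who fail before responding, of 10% to 30%.

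**Counting example.** Of 20 participants, 6 are rescued early and 6 of the other 14 later respond. With rescue censored, the curve reaches 6/14 = 42.9%. The share who responded is 6/20 = 30.0%.

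**Closed form.** Assume constant hazards and scale 50 weeks to 1.
- Total hazard = −ln(1 − p − q)
- Response hazard λ = total × p/(p + q); failure hazard μ = total − λ
- Planned estimate with failures censored: 1 − KM = 1 − exp(−λ)

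For p = 40%, q = 30%: total = −ln(0.30) = 1.204; λ = 1.204 × 4/7 = 0.688; 1 − exp(−0.688) = 49.7%, against 40%.

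| p (cumulative incidence) | 1 − KM, q = 10% | q = 20% | q = 30% |
|---|---|---|---|
| 20% | 21.2% | 22.5% | 24.2% |
| 30% | 31.8% | 34.0% | 36.8% |
| 40% | 42.6% | 45.7% | 49.7% |
| 50% | 53.4% | 57.7% | 63.4% |

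The excess runs from 1.2 points (p = 20%, q = 10%) to 13.4 points (p = 50%, q = 30%).

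**Against the rule in the note under Table 1.** If participants are followed through the event and then respond at hazard rλ, the Week 50 share is p + ∫₀¹ μ exp(−(λ + μ)t)[1 − exp(−rλ(1 − t))] dt. For p = 40%, q = 30% (μ = 1.204 − 0.688 = 0.516), this is 45.5% for r = 0.5, 49.7% for r = 1 and 55.8% for r = 2. The planned 49.7% can therefore be too high, right or too low.

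**Difference between arms.**
- More failure on placebo (ravulizumab p = 50%, q = 10%; placebo p = 30%, q = 30%): the 20.0-point difference becomes 53.4% − 36.8% = 16.6 points.
- Equal response of 40% with q of 30% against 10%: a difference of 7.2 points appears (49.7% against 42.6% before rounding), favouring the arm with more failures.

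For scale, in the first case the standard error of the difference with 40 and 20 participants is √(0.5 × 0.5/40 + 0.3 × 0.7/20) = √0.01675 = 12.9 points.

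**The case against.** A reader might infer that all three curves overstate response whatever the estimand, that all three contradict the SAP's rules, and that the treatment effect is therefore inflated. The documents do not support that.

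- **Direction.** Overstatement is certain against a nonresponder rule, for CRR/PRR after rescue, and for death. For time to UPCR ≤ 0.5 g/g the governing text is the note under Table 1, and against it the direction is open.
- **Contradiction.** SAP 5.5.5 and 5.5.7 are exploratory. The rules in SAP 5.1.4 are written for secondary endpoints, SAP 5.5 allows exceptions stated in its subsections, and Protocol 9.4.5.1 prescribes censoring at discontinuation and rescue. What remains for 5.5.5 is the clash with the CRR/PRR definition. No SAP responder rule names death, so for death the problem is one of competing risks.
- **Estimand preference.** The SAP assumes missing at random after discontinuation in the primary analysis and the MMRMs, and after rescue in the second MMRM version (SAP 5.4.1, 5.4.2). Censoring is the time-to-event counterpart. Reasons for stopping drug include pregnancy and study termination (Protocol 7.1), so stopping is not always failure. This is fair, but such an estimand has to be stated, and for time to UPCR the SAP states another.
- **Agreement with responder rates.** The curves use spot urine; CRR/PRR at Weeks 26 and 50 use 24-hour collections. They would differ under any censoring rule.
- **Log-rank test.** With competing events censored, it remains a valid comparison of cause-specific hazards. The fault lies in reading the curve as a response probability.
- **Weight.** The analyses are descriptive, and in the first worked example the arm difference moves by 3.4 points against a standard error of 12.9.

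**Conclusion.** The concern stands in limited form, with modest impact.

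1. Time to UPCR ≤ 0.5 g/g: SAP 5.4.6 and the note under Table 1 give incompatible handling of rescue and discontinuation, and nothing reconciles them.
2. Time to CRR and PRR: censoring at rescue is incompatible with a definition that excludes rescued participants, so one minus Kaplan-Meier overstates the share responding.
3. Death: the same overstatement applies in all three analyses.

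The 1 to 13 point excess rests on assumed response and failure rates and on constant hazards. It counts every event in q as precluding response. The effect on the arm difference has no fixed sign. These analyses carry no multiplicity-controlled claim (SAP 5.4, 5.5), so the primary conclusion is untouched.

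**What to change.** State one estimand for each time-to-response endpoint in or beside SAP Table 1.

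- **Time to CRR and PRR (5.5.5):** report the Aalen-Johansen cumulative incidence with rescue and death as competing events. Treat discontinuation and withdrawal as nonresponse, as SAP 5.4.4, 5.4.5 and 5.5.6 already do.
- **Time to UPCR ≤ 0.5 g/g (5.4.6):** either follow participants through rescue and discontinuation as the note under Table 1 says, with death as a competing event, or amend the note and use the nonresponder and competing-event handling.
- **Time to > 50% UPCR decrease (5.5.7):** state which of these two choices applies.
- **All three:** keep the currently planned Kaplan-Meier curve as a labelled sensitivity analysis, and keep the log-rank test described as a cause-specific comparison.
- **Appendix 5 (6.5):** record the departure from Protocol 9.4.5.1.

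The cost is SAP wording and a small change to the censoring derivation. No new data are needed: participants who stop study drug are asked to continue visits to Week 50 (Protocol 7.1), and those with Treatment Failure may stay in the study (Protocol 3.2.4).
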